### 3.2.2.1 Inclusion Criteria

The inclusion criteria are described in [Table 4](#). Patients will be included into this study only if all the inclusion criteria are met. These inclusion criteria define the overall study population.

**Table 4 Inclusion Criteria**

	Inclusion Criteria	Operational Definition
1	Patient aged $\geq 1$ year of age at CED	Aged $\geq 1$ year at CED
2	Patient has $\geq 1$ RTI episodes during the 12-month baseline period prior to CED	$\geq 1$ RTI episodes within a 12-month period during the inclusion period. The CED is the date of the 2 nd , 3 rd , ... or n th RTI episode (i.e., date of fulfilling the inclusion criteria). If one patient has multiple CED during the inclusion period, the CED will be selected randomly. The definition of an RTI episode provided in Section 3.3.2.1
3	Patient has $\geq 12$ months of continuous enrolment in the database prior to CED	$\geq 12$ months of continuous enrolment in the database prior to the CED. Operationally, patients were required to have entered the database at least 12 months before the CED to be included in the study. In THIN (Belgium and Italy), this can be defined by a district variable for entry to the database: first contact date. In Inspur (China), patients are required to have records in the database at least 12 months before the CED (during the 12-month baseline period) to be eligible for inclusion
4	No record of a prescription of any bacterial lysates in the 12-month baseline period prior to CED	No record of the country-specific drug codes ( Appendix 4 ) during the 12-month baseline period

Note: CED: cohort entry date; RTI: respiratory tract infection; THIN: The Health Improvement Network.

Inclusion criterion 2 on the requirement of having  $\geq 1$  prior RTI episodes is important to apply because OM-85 is indicated for prevention of recurrent RTIs (24). However, patients in the SOC/non-user comparator group may still have fewer prior recurrent RTIs than the OM-85 group receiving preventive therapy. Therefore, prior recurrent RTIs will also be used in the PS matching of the compared exposure groups. The impact (preventive effect) of OM-85 on the recurrence of RTIs is anticipated to be higher in patients with an increased recurrence risk (35). Hence, the analyses will also be stratified by the number of RTI episodes prior to CED (see [Table 5](#)).

The inclusion of patients is not defined by sex. Sex is instead defined at CED and considered in the PS.

### 3.2.2.2 Exclusion Criteria

No exclusion criteria will be applied.

### 3.2.2.3 Sub-Populations

In addition to analyses in the overall study populations, the following subgroup analysis will be considered. If conducted, all objectives may be assessed in several sub-populations, including **CCI** for the exploratory objectives, stratifications, and subgroups of interest ([Table 5](#)). Analyses in these sub-populations will be performed only where patient counts allow, considering data protection regulations to mask results if the cell count is small, e.g.,  $< 5$  patients.

**Table 5 Sub-Populations, Stratifications and Objectives for Which They Are Applied**

Sub-Populations	Operational Definition	Objectives In Which Applied
Sub-population of patients who had CCI [REDACTED]		
CCI [REDACTED] CCI [REDACTED]	CCI [REDACTED] CCI [REDACTED]	
 
Exploratory objectives CCI only
 

Stratifications and subgroup considering the CCI [REDACTED]		
CCI [REDACTED] CCI [REDACTED] CCI [REDACTED] CCI [REDACTED] CCI [REDACTED] CCI [REDACTED] CCI [REDACTED] CCI [REDACTED] CCI [REDACTED] CCI [REDACTED] CCI [REDACTED] CCI [REDACTED] CCI [REDACTED] CCI [REDACTED] CCI [REDACTED] CCI [REDACTED] CCI [REDACTED]	CCI [REDACTED] CCI [REDACTED] CCI [REDACTED] CCI [REDACTED] CCI [REDACTED] CCI [REDACTED] CCI [REDACTED] CCI [REDACTED] CCI [REDACTED] CCI [REDACTED]	
 
Exploratory objectives CCI only
 

Other stratifications		
Age at CED: 5 strata 
 
≥ 1 to < 6 years of age
 
≥ 6 to < 12 years of age
 
≥ 12 to < 18 years of age
 
≥ 18 to < 65 years of age
 
≥ 65 years of age
 
	Based on age at CED	
 
All objectives
 

Number of RTI episodes prior to CED: 2 strata 
 
≥ 1 to ≤3 RTI episodes
 
> 3 RTI episodes
 
	Based on number of RTI episodes during the 12-month baseline period	
 
All objectives
 

Subgroups of patients with selected comorbidities at CED		
CCI [REDACTED] CCI [REDACTED] Patients with allergic rhinitis at CED Patients with atopic dermatitis at CED Patients with food allergy at CED	≥ 1 record of ICD-9/ICD-10 codes defined in Appendix 3, during the maximum baseline period	
 
All objectives
 
Additionally stratified by the above 5 age categories
 

Vulnerable populations (subgroups) at CED		
Patients who were estimated to be pregnant at CED	Ongoing pregnancy and delivery/abortion are defined by ICD-9/ICD-10 codes as in Appendix 3 . Patients are estimated to have	
 
All objectives
 

	
been pregnant at CED if they fulfil any of the following definitions:
 
≥ 1 record of ICD-9/ICD-10 codes for ongoing pregnancy within 6 months before CED AND no record of delivery or abortion within 6 months before CED
 
OR
 
≥ 1 record of ICD-9/ICD-10 code for ongoing pregnancy at CED or during follow-up, at longest 6 months after CED
 
OR
 
≥ 1 record of ICD-9/ICD-10 code for abortion at CED or during follow-up, at longest 3 months after CED
 
OR
 
≥ 1 record of ICD-9/ICD-10 code for delivery at CED or during follow-up, at longest 9 months after CED
	
Patients aged ≥ 65 years at CED	Based on age at CED	
Patients aged ≥ 80 years at CED	Based on age at CED	
Patients with immunocompromised conditions at CED	≥ 1 record of ICD-9/ICD-10 codes or ATC codes defined in Appendix 6, during the maximum baseline period or shorter as detailed in Appendix 6	
Subgroups of OM-85 initiators based on OM-85 treatment cycle length and number		

OM-85 initiators, who had
 
 
• 1 treatment cycle of < 90 days
 
• 1 treatment cycle of 90 days 
 
• 1 treatment cycle of > 90 days to ≤ 180 days
 
• 1 treatment cycle of > 180 days
 
• 2 treatment cycles
 
	Defined based on the variables described in Section 3.3.1.2	
 
• Primary objective 1, secondary objective 3
 

Note: ATC: Anatomical Therapeutic Chemical; **CCI**; CED: cohort entry date; **CCI**; **CCI**; COVID-19: coronavirus disease 2019; ICD-9: ICD-10: International Statistical Classification of Diseases and Related Health Problems 9th Revision; International Statistical Classification of Diseases and Related Health Problems 10th Revision; RTI: respiratory tract infection.

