### 2.1 Primary Objectives

- **Primary objective 1: RTI rate 12 months before and 12 and 24 months after initiating OM-85:** To describe and compare the rate of RTIs episodes 12 months before initiating preventive treatment with OM-85 and 12 and 24 months after the initiation.
- **Primary objective 2: Comparative effectiveness – rate of RTI episodes during follow-up at 12 and 24 months:** To compare the rate of RTI episodes during the follow-up at 12 and 24 months, in patients initiating preventive treatment with OM-85 and in comparable patients not initiating OM-85 (SOC/non-user group).

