- **CED:** The CED is defined during the inclusion period, as the date of the 2nd, 3rd, ... or nth RTI episode during the inclusion period (see inclusion criteria in [Section 3.2.2](#)). This is also the date when a patient fulfils all the eligibility criteria. The CED can occur any time during the inclusion period. If a patient meets the eligibility criteria more than once during the inclusion period, and thereby has several candidate CEDs, the CED used in the study will be selected at random, which is one of the unbiased methods of selection of index date (29). The CED defines the end of the baseline period and the start of the initiation grace period for each included patient.

- **Baseline period:** The baseline period for each included patient is defined as the time before the CED. The minimum baseline period will be 12 months, and the maximum baseline period will be as long as data are available in each country (from January 2005 in Belgium, from January 1994, for GPs and 2017 for paediatricians, in Italy, and from January 2018 in China). The minimum baseline period of 12 months will be used for assessing the RTI rate during the baseline period and other baseline variables ([Section 3.7.4.1](#)). The maximum baseline period (all available data) will be used for selected variables, such as comorbidities (e.g., allergies, myocardial infarction, and cancer, see [Table 8](#)), since these could have occurred earlier but may not have been recorded in the data during the 12-month baseline period. Extending the 12-month baseline period for such variables is expected to improve the accurate classification of them (i.e., decreases the risk of covariate misclassification).
- **Initiation grace period:** For each included patient, a 30-day initiation grace period starting from the CED will be applied, to allow the included patients to initiate OM-85 during a reasonable period after the CED, as it is unrealistic to expect that OM-85 would in clinical practice be prescribed on the date of meeting the eligibility criteria ([28,29](#)).
- **OM-85 initiation date:** The OM-85 initiation date will be the date of the first observed prescription of OM-85 during the 30-day initiation grace period, starting from the CED. This is applicable only for the OM-85 exposure group.

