**Table 3 Populations for Each Study Objective**

Objective		Population In Which Studied and Index Date
Primary objectives		
1	RTI rate 12 months before and 12 and 24 months after initiating OM-85	
 
OM-85 initiators only, within the overall study population
 
Index date: OM-85 initiation date
 

2	Comparative effectiveness – rate of RTI episodes during follow-up at 12 and 24 months	
 
Both exposure groups (OM-85 initiators and SOC/non-user group) within the overall study population
 
Index date: end of initiation grace period
 

Secondary objectives		
1	Patient characteristics at CED	
 
Both exposure groups (OM-85 initiators and SOC/non-user group) within the overall study population
 
Index date: CED
 

2	Descriptive pattern of prescribing OM-85	
 
OM-85 initiators only, within overall study population
 
Index date: OM-85 initiation date
 

3	RTI rate 12 months before and 6 and 9 months after initiating OM-85	
 
OM-85 initiators only, within the overall study population
 

Objective		Population In Which Studied and Index Date
		
 
Index date: OM-85 initiation date
 

4	Comparative effectiveness – rate of RTI episodes during follow-up at 6 and 9 months	
 
Both exposure groups (OM-85 initiators and SOC/non-user group) within the overall study population
 
Index date: end of initiation grace period
 

5	Descriptive pattern of prescribing antibiotics during follow-up	
 
Both exposure groups (OM-85 initiators and SOC/non-user group) within the overall study population
 
Index date: end of initiation grace period
 

6	Descriptive pattern of concomitant medications of interest during follow-up	
 
Both exposure groups (OM-85 initiators and SOC/non-user group) within the overall study population
 
Index date: end of initiation grace period
 

7	Descriptive healthcare resource utilisation during follow-up	
 
Both exposure groups (OM-85 initiators and SOC/non-user group) within the overall study population
 
Index date: end of initiation grace period
 

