### **3.7.3 Analysis of Primary Endpoint: RTI Rates (Primary Objectives 1-2, Secondary Objectives 3-4, Exploratory Objectives CCI)**

The primary outcome is the rate of RTIs episodes measured during different periods of interest, as specified in the objectives. The rate of RTI episodes will be estimated by calculating the total number of RTI episodes observed, divided by the total number of person-time (e.g., person-years) during a period of interest. Rates of RTI episodes will be estimated separately in patients initiating preventive treatment with OM-85 and in the SOC/non-user group. Furthermore, rates of RTI episodes during the baseline period will serve as reference in each treatment group to evaluate the effects of therapy during follow-up.

Comparative analysis comparing the RTI rates before and after OM-85 initiation, and analysis comparing RTI rates in the two exposure groups will be performed using approaches as described in the General Considerations. Generalised linear models with a Poisson distribution or negative binomial distribution (to account for over-dispersion) will be used to estimate the association between the initiation of OM-85 and the outcome of RTI rates, with the natural logarithm of the time at risk as offset (42).

The analyses will be identical for the exploratory objectives **CCI** **CCI** (Section 3.2.2.3).

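### Splitting the before-after RTI rate ratio by the baseline RTI count selects patients on the ratio's own denominator, so the stratum results cannot be read as effect modification

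*Protocol*

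**What the plan says.** Table 5 (Section 3.2.2.3) lists "Number of RTI episodes prior to CED: 2 strata", namely 1 to 3 and more than 3. It defines them "Based on number of RTI episodes during the 12-month baseline period" and enters all objectives in the last column. Other rows of the table are limited to named objectives; the OM-85 cycle-length subgroups, for example, apply only to primary objective 1 and secondary objective 3.

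The reason for the split is given in Section 3.2.2.1: "The impact (preventive effect) of OM-85 on the recurrence of RTIs is anticipated to be higher in patients with an increased recurrence risk". The next sentence reads "Hence, the analyses will also be stratified by the number of RTI episodes prior to CED". Section 3.2.2.3 is less firm and makes the subgroup work conditional.

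The reference window for the before-after rate ratio is described in two ways:
- **Ending at the cohort entry date (CED).** Section 3.2.1: "The minimum baseline period of 12 months will be used for assessing the RTI rate during the baseline period and other baseline variables". Section 3.7.3: "rates of RTI episodes during the baseline period will serve as reference in each treatment group to evaluate the effects of therapy during follow-up". Table 8 likewise measures the rate for secondary objectives 3 and 4 at the 12-month baseline.
- **Ending at OM-85 initiation.** Section 2.1 sets the reference as "the rate of RTIs episodes 12 months before initiating preventive treatment with OM-85", and Table 3 gives, for primary objective 1, "Index date: OM-85 initiation date". Initiation falls 0 to 30 days after the CED.

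**The concern.** A patient reaches the upper stratum by having a high count in the reference year. Part of any such count is chance and is not repeated in the following year, so the after/before ratio in that stratum falls with no help from the drug. The lower stratum is selected on the same quantity from the other side. A difference between the two before-after ratios is thus built in by the way the strata are formed.

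This is the split for which Section 3.2.2.1 states an expected direction, and under one of the two window definitions the artefact points the same way. Section 3.9.1.1 lists disease progression, changes in care and access, and changing infection rates as threats to the before-after design. It names neither regression to the mean nor selection on the baseline count. The only caution attached to a subgroup in Table 5 (footnote 3) concerns cycle length. A stratum difference could therefore be reported as effect modification with nothing in the plan to warn against it.

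**Working it through.** **Inputs from the protocol.** Baseline rate 2 episodes per person-year and equal person-time (Section 3.5); strata 1 to 3 and more than 3 (Table 5); 14-day maximum episode length (Section 3.3.2.1); CED drawn at random among qualifying episodes and initiation within 30 days (Section 3.2.1). Between-patient heterogeneity is not given. I assume gamma-distributed patient rates with shape k, from none (Poisson) down to k = 0.5; Section 3.7.3 itself allows for over-dispersion.

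**The plan's own figure.** With b = 2 × PY and a = IRR × b, the F-based interval of Section 3.5 reproduces all 32 cells of Table 9. At IRR 0.9 and 350 PY (b = 700, a = 630) the width is 0.197; at 300 PY it is 0.213. That table describes sampling precision only and is silent on selection.

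**Overlap of the windows.** If the window ends at the CED, the stratifying count is the reference count. If it ends at initiation, the overlap is at least 365 − 30 = 335 days, and the CED episode itself enters the reference count whenever initiation follows the CED.

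**Simple model, inert drug, window ending at the CED.** With before-count y and mean μ = 2, E[after | y] = (k + y)μ/(k + μ), or simply μ under Poisson.
- Poisson: mean y is 1.875 in the 1 to 3 stratum and 4.53 above 3. The ratios are 2/1.875 = 1.07 and 2/4.53 = 0.44.
- k = 1: mean y is 1.74 and 6.0. Expected after-counts are 2.74 × 2/3 = 1.82 and 7.0 × 2/3 = 4.67. The ratios are 1.05 and 0.78.

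The full range is 1.07 against 0.44 (Poisson) to 1.04 against 0.86 (k = 0.5).

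**Simulation of the protocol's rules, inert drug, 2 per year.** Random CED, 14-day episodes, a 3.5-year inclusion period, initiation after the CED within 30 days, 12 months of follow-up, stable patient rates. Before-after IRR, 1 to 3 against more than 3:

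| Heterogeneity | 12 months before CED | 12 months before initiation |
|---|---|---|
| Poisson | 0.91 vs 0.37 | 0.58 vs 0.31 |
| k = 2 | 0.91 vs 0.66 | 0.58 vs 0.56 |
| k = 1 | 0.94 vs 0.75 | 0.59 vs 0.65 |
| k = 0.5 | 0.95 vs 0.84 | 0.60 vs 0.74 |

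A second run gave 0.91 to 0.94 against 0.37 to 0.85 for the CED window and about 0.59 against 0.31 to 0.74 for the initiation window, so the second decimal carries simulation error.

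**Ratio of the two stratum IRRs (upper divided by lower).** With the CED window it is about 0.41 to 0.90, below 1 in every scenario. With the initiation window and initiation after the CED it is 0.53 to 1.23; adding year-to-year variation in patients' rates gives 0.60 to 0.99. If OM-85 is prescribed on the CED itself, the two windows coincide and the ratio is 0.43 to 0.90.

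**The case against.** The strongest reply is that the direction is not assured. Table 3 anchors primary objective 1 to OM-85 initiation, and Section 3.1.1 says that requiring initiation at the CED would leave very few OM-85 patients, so most initiate later. The CED episode then enters the reference count and inflates it proportionally more in the low stratum. The table above shows the gradient close to zero at k = 2 and reversed at k = 1 and below. This stands. A reader might infer that an ineffective drug is bound to look much better above 3 episodes, that the false reduction is confined to that stratum, and that the protocol's expectation would be falsely confirmed. The documents do not support that: it depends on which window is used and on a heterogeneity they do not give, and under the initiation window the low stratum also shows a false reduction of about 40%.

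It can also be said that Section 3.2.2.3 makes the subgroup work conditional, Section 3.7.6 leaves detail to the SAP, Section 3.1.1 presents the before-after design as reference data, Section 3.9.1.1 asks for caution, and no before-after interaction test is announced. This limits the weight of the point. It does not remove it: Section 3.2.2.1 says the stratification will be done, Table 5 assigns it to every objective, and a conditional analysis is no more valid once run. Nor does the protocol state any intention to claim a target population from this split.

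**Conclusion.** The point holds in limited form. Before-after rate ratios by baseline-count stratum are distorted by selection on their own reference count under either definition of the window, and a difference between strata cannot be read as effect modification. With the 12 months before the CED as reference, the false reduction above 3 episodes is 15% to 63% (1 − 0.85 to 1 − 0.37), against 6% to 9% in the lower stratum. That resembles the anticipated pattern, and it exceeds the 10% reduction (IRR 0.9) used for the precision planning. With the initiation window both strata are biased downwards and the sign of the contrast is indeterminate.

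These sizes rest on 2 episodes per year, stable patient rates and the assumed heterogeneity range. The point concerns the stratified before-after results only. In the OM-85 versus SOC comparison both groups are selected on the same count, so this artefact does not arise there by itself.

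**What to change.** In Table 5, limit the stratification of RTI-rate effects by number of RTI episodes before the CED to the OM-85 versus SOC comparison (primary objective 2, secondary objective 4), tested with an exposure-by-stratum interaction term. Remove primary objective 1, secondary objective 3 and any other before-after objective from that row. Reconcile the reference window in Sections 3.2.1 and 3.7.3 and Table 8 with that in Section 2.1 and Table 3.

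Forming the before-after strata from RTIs in months 13 to 24 before the CED is not a remedy. Patients still enter on at least one RTI in the reference year, which inflates the reference most where rates are low. For an inert drug at k = 1, the ratios in the lower and upper strata become 0.81 against 1.02 (CED window) or 0.54 against 0.83 (initiation window), a false gradient in the opposite direction.

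The cost is one table entry, matching SAP wording, and the loss of one descriptive before-after split. The question of whether the effect varies with RTI history is kept, in the analysis that has a comparator.

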**CCI**

**CCI**

**CCI**

**CCI**

**CCI** The dates provided in [Table 5](#) applies to the Tianjin Province.

 While these subgroups are formed based on OM-85 treatment cycle length and number, the analyses shall be reported with caution because patients who had data available for longer (e.g., longer cycle length) may represented a healthier population, as they had survived longer than the ones with shorter length.

 If few patients have a treatment cycle length of exactly 90 days, this category may be collapsed with the first category.

### 3.3 Variables

Exposures, outcomes and other variables used in the study are detailed in this section. Drugs used for definitions of exposure and other variables will be defined using the Anatomical Therapeutic Chemical (ATC) Classification System in THIN Belgium, the Autorizzazione all'Immissione in Commercio (AIC) code in Italy (marketing authorisation code) and brand names in China. Data on drug use represents prescription records only, as no dispensing records are available in THIN Belgium and Italy, and Inspur (China). Diagnoses used for definitions of outcomes and other variables will be defined using the 10th revision of the International Statistical Classification of Diseases and Related Health Problems (ICD-10) in China and Belgium, and both ICD-10 and the 9th revision (ICD-9) in Italy, as applied in each country.

To assess whether the data source contains the needed data elements, the variables to be assessed were selected based on the needs of the research objectives of the full study and the comprehensive feasibility assessment was conducted. The data sources were requested to quantify the availability of the data elements in the data source and if additional patient data are accessible from the originating source(s). If either of these criteria were fulfilled, the variable was considered available. The availability of variables was completed for all data sources.

#### 3.3.1 Exposures

To investigate the effectiveness of OM-85 using the TTE framework, the other clinically relevant treatment strategy that OM-85 will be compared to needs be defined, i.e., a treatment strategy that the patients prescribed OM-85 could alternatively have (28,29). This alternative treatment strategy to patients who initiated OM-85 is defined as “not initiating OM-85”, which will represent a SOC/non-user group (Table 6).

A 30-day initiation grace period starting from the CED will be applied for each included patient (Section 3.2.1), to allow the included patients to initiate OM-85 during a reasonable period after the CED, as it is unrealistic to expect that OM-85 would in clinical practice be prescribed on the date of meeting the eligibility criteria (28,29). Patients will be ascertained as treated or untreated depending on whether they received a prescription for OM-85 during the grace period.

After the patients have been categorised to one of the treatment strategies during the initiation grace period, the OM-85 treatment strategy will be considered static and no censoring will be applied due to “deviation from the treatment strategy”. Censoring at initiation of other treatments for RTI will not be applied, because patients initiating OM-85 are typically prescribed RTI

treatments as part of RTI treatment pathway, including symptomatic measures and/or antibiotics. In other words, patients in clinical practice may be prescribed other treatments in parallel with OM-85. Therefore, censoring at initiation of another therapy would not be a deviation from the OM-85 treatment strategy. Censoring OM-85 at discontinuation will also not be applicable, because OM-85 is not used continuously in clinical practice, but rather as 3-month or 6-month courses (consisting of monthly 10-days treatment periods). Consequently, all patients initiating OM-85 will be followed-up regardless of initiation or parallel use of other therapies.

The frequency of RTI episodes could be impacted by other treatments taken during the follow-up. However, it is likely that most patients co-medicate over the course of RTI episodes, which would lower the magnitude of effect. To address this limitation, the results will be interpreted considering observed other treatments than the index drug during the follow-up period.

In the SOC/non-user group, patients are censored at the date of observing a record of an OM-85 prescription, as the SOC/non-user patients would then deviate from their treatment strategy.

